10.2 Handling of Multiplicity

There will be no hypothesis testing for the primary and secondary efficacy endpoints. Therefore, there will be no adjustment for multiple comparisons.

10.3 Primary PK and Primary Efficacy Analysis

10.3.1 Primary PK Analysis

The primary pharmacokinetic endpoint will be the steady state AUC of GLE and PIB estimated by non-compartmental pharmacokinetic analysis or population pharmacokinetic analysis. The 95% confidence interval for the geometric mean of AUC values will be calculated. For subjects enrolled in Japan, the pharmacokinetic parameters will be summarized separately.

10.3.2 Primary Efficacy Analysis

For US regulatory agency the efficacy endpoint of SVR₁₂ (HCV RNA < LLOQ 12 weeks after the last actual dose of study drug) across all subjects in the ITT population is considered primary efficacy endpoint. For all other regulatory agencies the SVR₁₂ efficacy endpoint is considered secondary.

The number and percentage of subjects achieving SVR₁₂ will be summarized along with a two-sided 95% confidence interval using the normal approximation to the binomial distribution, unless the number of SVR₁₂ non-responders is less than 5, where the Wilson's score method¹ will be used to calculate the confidence interval instead.

A summary of reasons for SVR₁₂ non-response (e.g., on-treatment virologic failure, relapse, other) will be provided. A listing of subjects who do not achieve SVR₁₂ by reason for non-response will also be provided.

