**Statistical Methods (Continued):**

**Efficacy:**

The secondary endpoint is the percentage of subjects who achieve SVR12 overall and by age group. The percentage will be calculated along with a 2-sided 95% confidence interval calculated using the normal approximation to the binomial distribution, unless the number of subjects who fail to achieve SVR12 is less than 5, where the Wilson's score method will be used for the confidence interval instead.

Additional secondary endpoints include the percentage of subjects who experience post-treatment relapse, the percentage of subjects who experience on-treatment virologic failure (i.e., breakthrough or failure to suppress at the end of treatment), and the percentage of subjects with new HCV infection (i.e., re-infection) at any time up to the last study visit.

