### **8.1.2.2 Secondary Endpoints**

The secondary endpoints are:

1.  $C_{max}$  and clearance of GLE and PIB at Week 2;
2. The percentage of subjects with SVR12 by age group and overall;
3. The percentage of subjects with on-treatment virologic failure (i.e., breakthrough, defined as confirmed increase of  $> 1 \log_{10}$  IU/mL above nadir during treatment or confirmed HCV RNA  $\geq 100$  IU/mL after HCV RNA  $< \text{LLOQ}$  during treatment, or HCV RNA  $\geq \text{LLOQ}$  at the end of treatment with at least 6 weeks of treatment) by age group and overall;
4. The percentage of subjects with post-treatment relapse (defined as confirmed HCV RNA  $\geq \text{LLOQ}$  between end of treatment and 12 weeks after the last dose of study drug among subjects who completed treatment as planned with HCV RNA  $< \text{LLOQ}$  at the end of treatment; excluding subjects who have been shown to be re-infected) by age group and overall;
5. The percentage of subjects with new HCV infection (i.e., re-infection) at any time up to the last visit by age group and overall;
6. Assessment of palatability/acceptability of the pediatric formulation by age group and overall.

The number and percentage of subjects achieving SVR12 will be summarized along with a two-sided 95% confidence interval using the normal approximation to the binomial distribution, unless the number of subjects who fail to achieve SVR12 is less than 5, where the Wilson's score method will be used for the confidence interval instead.

In addition, a summary of reason for SVR12 non-response (e.g., on-treatment virologic failure, relapse, reinfection, other) will be provided for each age group.

For the analysis of on-treatment virologic failure, relapse, and re-infection, the number and percentage of subjects will be summarized along with a two-sided 95% confidence interval using Wilson's score method.

For the analysis of post-treatment HCV virologic relapse, completion of treatment is defined as any subject with study drug duration of 52 days, 77 days, and 103 days or greater for subjects allocated to treatment durations of 8 weeks, 12, and 16 weeks, respectively.

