10.5 Sensitivity Analysis for SVR

As sensitivity analysis, the number and percentage of subjects in the mITT-VF population achieving SVR₁₂, as applicable, will be summarized, along with a two-sided 95% confidence interval using Wilson's score method.

As a sensitivity analysis, a two-sided 95% confidence interval for the SVR₁₂ rate in the ITT population will be calculated using a Wilson score interval if that was not used in the primary analysis.

A listings of subject excluded from the mITT-VF population will be provided.

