10.7 Additional Efficacy Analyses

The following additional efficacy endpoints will be summarized and analyzed for the ITT population:

- The percentage of subjects with HCV RNA $< \text{LLOQ}$ at each post-baseline visit in the Treatment Period (using data as observed) by age group and overall;
- The percentage of subjects with SVR₁₂ by age group;
- The percentage of subjects with SVR₄ by age group and overall;

- The percentage of subjects with SVR₂₄ by age group and overall;

All rates will be presented with two-sided 95% confidence intervals using the Wilson's score method.

A summary of the subjects who completed treatment and relapsed (defined as **Relapse_{overall}**) will be prepared displaying the number of subjects relapsing overall and by SVR visit window (within the SVR₄, SVR₁₂, SVR₂₄ windows or after SVR₂₄ window), including the subject number and the SVR visit window corresponding to the first HCV RNA value of those indicating the occurrence of relapse. A similar listing will be prepared for subjects who prematurely discontinued treatment and relapsed after having HCV RNA < LLOQ at their Final Treatment Visit. A listing of subjects in the ITT population excluded from the relapse denominator (e.g., study drug duration < 52 days for subjects assigned to 8 weeks of treatment) will be provided, as applicable.

The number and percentage of subjects who do not achieve SVR₂₄ will be summarized by reason for non-response (as defined in Section 10.1). A listing of subject numbers and reason for non-response will be prepared.

The concordance between SVR₁₂ and SVR₂₄ will be assessed by the agreement between SVR₁₂ and SVR₂₄ and the positive predictive value (PPV) and negative predictive value (NPV) of SVR₁₂ on SVR₂₄. The agreement between SVR₁₂ and SVR₂₄ is a percentage defined as the number of subjects achieving both SVR₁₂ and SVR₂₄ and the number of subjects where both SVR₁₂ and SVR₂₄ are not achieved. The PPV of SVR₁₂ on SVR₂₄ is the proportion of subjects who achieve SVR₂₄ out of all subjects who achieved SVR₁₂. The NPV of SVR₁₂ on SVR₂₄ is the proportion of subjects who do not achieve SVR₂₄ out of all subjects who did not achieve SVR₁₂. Similarly, the concordance between SVR₄ and SVR₁₂ will be summarized.

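### The interval for overall SVR12 changes method at five non-responders, so a fifth failure raises both 95% limits by 0.5 to 0.8 points

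*SAP*

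**What the plan says.** SAP 10.3.2 makes SVR12 across all ITT subjects the primary efficacy endpoint for the US agency and a secondary endpoint elsewhere. Its two-sided 95% interval is obtained "using the normal approximation to the binomial distribution, unless the number of SVR₁₂ non-responders is less than 5"; in that case Wilson "will be used to calculate the confidence interval instead". Protocol 8.1.2.2 has the same switch ("where the Wilson's score method will be used for the confidence interval instead"), and so does the protocol synopsis ("a 2-sided 95% confidence interval calculated using the normal approximation to the binomial distribution", with the same exception).

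Three other provisions bear on the point:

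- SAP 10.5 plans a sensitivity interval for SVR12 in the ITT population that "will be calculated using a Wilson score interval if that was not used in the primary analysis". Protocol 8.1.2.5 also asks for a Wilson interval on the ITT population as a sensitivity analysis.
- SAP 10.2 states: "There will be no hypothesis testing for the primary and secondary efficacy endpoints".
- SAP 10.7 lists SVR12 by age group and says: "All rates will be presented with two-sided 95% confidence intervals using the Wilson's score method". Protocol 8.1.2.2 instead applies the switch to SVR12 by age group as well as overall. SAP 12.1 does not list this difference among its changes from the protocol.

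**The concern.** At high response rates the normal-approximation interval is centred on the estimate, while the Wilson interval is pulled towards 50%. Passing from Wilson to the normal approximation as failures go from four to five shifts the whole interval upwards by more than the extra failure moves it down. A trial with one more failure would then report a more favourable headline interval for its US primary efficacy endpoint.

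The switch lies within the plausible range of results. Protocol 3.2 allows that failure may be more frequent than in adults, and SAP 6.3 counts SVR12 data still missing after imputation as failure, so lost subjects add to the count. When the switch happens, the report carries a normal-approximation headline beside a visibly lower Wilson sensitivity interval.

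**Working it through.** **Inputs.** n is about 125 (protocol 8.2) or about 110 (SAP 4.2). Intervals are two-sided at alpha 0.05 (protocol 8.1), so z = 1.95996. The rule is Wilson for 0 to 4 failures and the normal approximation for 5 or more (SAP 10.3.2). The adult rate is 97.8% (2206/2256, protocol Table 3).

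**Formulas**, with p the observed SVR12 proportion and no continuity correction, since neither document mentions one:

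- Normal approximation: p ± z·√(p(1−p)/n)
- Wilson: [p + z²/(2n) ± z·√(p(1−p)/n + z²/(4n²))] / (1 + z²/n)

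**Formula check.** The documents give no planned interval for SVR12, so there is no such figure to reproduce. The normal-approximation formula does reproduce intervals in protocol Table 3: 274/281 gives 95.7 to 99.3, and 112/116 gives 93.2 to 99.9.

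**At the switch, n = 125.**

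- Four failures: p = 0.9680; Wilson centre 0.95405, half-width 0.03344; limits 92.06% to 98.75%.
- Five failures: p = 0.9600; half-width 1.95996 × √(0.96 × 0.04/125) = 0.03435; limits 92.56% to 99.44%.

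| n | Failures | Estimate (%) | Interval under the rule (%) | Wilson throughout (%) |
|---|---|---|---|---|
| 125 | 4 | 96.80 | 92.06 to 98.75 | 92.06 to 98.75 |
| 125 | 5 | 96.00 | 92.56 to 99.44 | 90.98 to 98.28 |
| 125 | 6 | 95.20 | 91.45 to 98.95 | 89.92 to 97.78 |
| 110 | 4 | 96.36 | 91.02 to 98.58 | 91.02 to 98.58 |
| 110 | 5 | 95.45 | 91.56 to 99.35 | 89.80 to 98.04 |
| 110 | 6 | 94.55 | 90.30 to 98.79 | 88.61 to 97.48 |

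From four to five failures the rule raises the lower and upper limits by 0.50 and 0.69 points (n = 125) or 0.54 and 0.77 points (n = 110). Wilson throughout lowers them by 1.08 and 0.47, or 1.22 and 0.53. At six failures the upper limit under the rule is still 0.20 or 0.21 points above its four-failure value. Continuity-corrected versions change the sizes, but both limits still rise.

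**Chance of reaching the switch** (exact binomial; 97% and 96% are assumptions):

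| True SVR12 | 5 or more failures, n = 110 / 125 | Exactly 5 or 6 failures, n = 110 / 125 |
|---|---|---|
| 97.8% (adult) | 9.6% / 14.2% | 8.5% / 12.1% |
| 97% | 23.5% / 32.2% | 18.7% / 23.9% |
| 96% | 45.0% / 56.3% | 29.8% / 32.8% |

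**Coverage** (exact, 1401-point grid of true rates):

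- True rates 0.92 to 0.99: mean coverage is 98.3% (n = 110) and 97.9% (n = 125) for the rule, against 95.5% for Wilson at both.
- True rates 0.95 to 0.99: the chance that the lower limit exceeds the truth is the same for both methods, at most 2.5%. Minimum coverage is 94.7% for the rule and 92.6% to 92.7% for Wilson.
- True rates from 0.92 to below 0.95, n = 125: the lower-limit miss rate reaches 6.4% for the rule and 2.6% for Wilson.

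**The case against.** The best defence is that nothing depends on this. There is no test, success threshold or SVR12 precision target, and the sample size is justified by pharmacokinetics. The rule is fixed in advance, leaves no discretion, and uses Wilson where the normal approximation is weakest. Whenever the normal approximation is the headline, the Wilson interval is reported too, so the proposal only changes which one is called primary. Any one trial has a single failure count, so no reader sees the four- and five-failure intervals together. Near the adult rate the rule also has better worst-case coverage than Wilson (94.7% against 92.6% to 92.7%).

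Most of this stands, and it limits the point to a recommended improvement. It does not remove it. The sensitivity interval shows the discrepancy but leaves the headline as it is. The coverage advantage for true rates of 0.95 to 0.99 comes from upper limits that are too high, since lower-limit misses are the same there. Below 0.95 the rule's lower limit is the less reliable one. The by-age-group disagreement is a separate matter of consistency and is not evidence for the main point, although the same edit settles it.

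**Conclusion.** The concern holds. At either planned sample size, the fifth non-responder raises both limits of the headline SVR12 interval by 0.50 to 0.77 points while the estimate falls by 0.80 (n = 125) or 0.91 (n = 110). This rests on the uncorrected formulas and applies to the overall analysis; the shifts differ in smaller groups. The probability of five or more failures is 9.6% to 14.2% at the adult rate and higher under the assumed lower rates.

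No conclusion of the trial is invalidated. The rule is conservative on average, and no excess lower-limit error is claimed for true rates of 0.95 to 0.99. The plan should be changed because the interval behaves illogically for the US primary efficacy endpoint and a consistent method is already planned for nearly every other rate.

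**What to change.** In SAP 10.3.2, protocol 8.1.2.2 and the synopsis, make the Wilson score interval the primary interval for SVR12 at every failure count. Keep the normal approximation only as a sensitivity analysis, if it is wanted. Edit SAP 10.5 and protocol 8.1.2.5 to match, because their ITT Wilson sensitivity interval becomes redundant. The protocol then also agrees with SAP 10.7 for SVR12 by age group.

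The cost is about one sentence in each place and no new programming. The protocol text would need an amendment, which under protocol 9.1 goes to the ethics committees, so it is best combined with another amendment. The statistical price is a lower headline limit once the switch point is reached: at five failures by 92.56 − 90.98, about 1.6 points (n = 125), or 91.56 − 89.80, about 1.8 points (n = 110); at six failures by about 1.5 or 1.7 points.

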10.4 Secondary PK and Efficacy Analyses

10.4.1 Secondary PK Analyses

The secondary PK endpoint is:

1. C_{max} and clearance of GLE and PIB

C_{max} and clearance values will be estimated by non-compartmental pharmacokinetic analysis or population pharmacokinetic analysis. For subjects enrolled in Japan, the pharmacokinetic parameters will be summarized separately.

10.4.2 Secondary Efficacy Analyses

The secondary efficacy endpoints are:

- The percentage of subjects with on-treatment HCV virologic failure (defined as **On-treatment virologic failure**) by age group and overall,
- The percentage of subjects with post-treatment HCV relapse (defined as **Relapse₁₂**; subjects with reinfection will be summarized separately) by age group and overall,
- The percentage of subjects with re-infection by age group and overall,
- Assessment of palatability of the pediatric formulation by age group and overall.

The number and percentage of subjects with on-treatment virologic failure, post-treatment relapse (**Relapse₁₂**) and re-infection will be summarized along with two-sided 95% confidence interval using Wilson's score method.

For the assessment of palatability, the number and percentage of subjects with each categorical answer marked will be presented for each question in the palatability questionnaire at each applicable treatment visit by age group and overall. A listing of acceptability questionnaire results and comments for each applicable subject over applicable treatment visits will be produced.

10.5 Sensitivity Analysis for SVR

As sensitivity analysis, the number and percentage of subjects in the mITT-VF population achieving SVR₁₂, as applicable, will be summarized, along with a two-sided 95% confidence interval using Wilson's score method.

As a sensitivity analysis, a two-sided 95% confidence interval for the SVR₁₂ rate in the ITT population will be calculated using a Wilson score interval if that was not used in the primary analysis.

A listings of subject excluded from the mITT-VF population will be provided.

10.6 Efficacy Subgroup Analysis

The percentage of subjects with SVR₁₂ in the ITT population will be calculated along with the corresponding 2-sided 95% Wilson score confidence interval for the following subgroups if applicable:

- HCV genotype (1, 2, 3, 4, 5, or 6);
- Prior HCV treatment history (treatment-naïve or treatment-experienced);
- For treatment-experienced subjects, type of previous regimen (IFN- or SOF-based);
- Sex (male or female);
- Race (black or non-black);

- Ethnicity (Hispanic or Latino, Not Hispanic or Latino);
- Geographic region (North America, Europe, Japan);
- Height z-score (< -1 , -1 to 1 or > 1);
- BMI z-score (< -1 , -1 to 1 or > 1);
- Drug compliance ($< 80\%$ versus $\geq 80\%$)
- Baseline fibrosis stage (F0 – F1, F2, F3 or F4);
- Cirrhosis status (yes/no);
- Baseline HCV RNA level ($< 1,000,000$, $\geq 1,000,000$ to $< 2,000,000$, $\geq 2,000,000$ IU/mL);
- Baseline platelet count (< 90 or $\geq 90 \times 10^9/L$);
- Baseline albumin (< 35 or ≥ 35 g/L);
- Injection drug user (yes, within last 12 months; yes, more than 12 months ago; or no);
- Concomitant use of Proton Pump Inhibitors (PPIs) (yes/no).
- Concomitant use of Statins (yes/no);

For subjects with cirrhosis only:

- Baseline Child-Pugh Score (5, 6, or > 6).
- Baseline platelets (< 90 or $\geq 90 \times 10^9/L$);
- Baseline albumin (< 35 or ≥ 35 g/L);

10.7 Additional Efficacy Analyses

The following additional efficacy endpoints will be summarized and analyzed for the ITT population:

- The percentage of subjects with HCV RNA $< \text{LLOQ}$ at each post-baseline visit in the Treatment Period (using data as observed) by age group and overall;
- The percentage of subjects with SVR₁₂ by age group;
- The percentage of subjects with SVR₄ by age group and overall;

- The percentage of subjects with SVR₂₄ by age group and overall;

All rates will be presented with two-sided 95% confidence intervals using the Wilson's score method.

A summary of the subjects who completed treatment and relapsed (defined as **Relapse_{overall}**) will be prepared displaying the number of subjects relapsing overall and by SVR visit window (within the SVR₄, SVR₁₂, SVR₂₄ windows or after SVR₂₄ window), including the subject number and the SVR visit window corresponding to the first HCV RNA value of those indicating the occurrence of relapse. A similar listing will be prepared for subjects who prematurely discontinued treatment and relapsed after having HCV RNA < LLOQ at their Final Treatment Visit. A listing of subjects in the ITT population excluded from the relapse denominator (e.g., study drug duration < 52 days for subjects assigned to 8 weeks of treatment) will be provided, as applicable.

The number and percentage of subjects who do not achieve SVR₂₄ will be summarized by reason for non-response (as defined in Section 10.1). A listing of subject numbers and reason for non-response will be prepared.

The concordance between SVR₁₂ and SVR₂₄ will be assessed by the agreement between SVR₁₂ and SVR₂₄ and the positive predictive value (PPV) and negative predictive value (NPV) of SVR₁₂ on SVR₂₄. The agreement between SVR₁₂ and SVR₂₄ is a percentage defined as the number of subjects achieving both SVR₁₂ and SVR₂₄ and the number of subjects where both SVR₁₂ and SVR₂₄ are not achieved. The PPV of SVR₁₂ on SVR₂₄ is the proportion of subjects who achieve SVR₂₄ out of all subjects who achieved SVR₁₂. The NPV of SVR₁₂ on SVR₂₄ is the proportion of subjects who do not achieve SVR₂₄ out of all subjects who did not achieve SVR₁₂. Similarly, the concordance between SVR₄ and SVR₁₂ will be summarized.

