6.3 Missing Data Imputation

Missing Data Imputation for SVR

HCV RNA values will be selected for analysis based on the analysis windows defined in Section 6.2.

For analyses of SVR, subjects' missing visit values will have backward imputation applied, if possible. For backward imputation, if the nearest HCV RNA value after the SVR window is unquantifiable or undetectable, then it will be used to impute the HCV RNA value in the SVR window. If a subject is missing an HCV RNA value within the appropriate SVR window after performing backward imputation, then this value will be imputed with an HCV RNA value from a local laboratory if present; otherwise, the HCV RNA value will be missing. Subjects with missing HCV RNA data in the analysis window, after imputations, will be imputed as a failure.

Regardless of the imputation method described above, if a subject starts another treatment for HCV, then all HCV RNA values for this subject measured on or after the start date of the new HCV treatment will be excluded from analyses. The subject will be considered a failure for summaries of viral response at all time points after the start of the new HCV treatment.

Missing Data Imputation for Virologic Failure

If HCV RNA values from the central laboratory are missing but a local laboratory value is present in the appropriate time period, then the local laboratory value will be used to assess post-treatment relapse and on-treatment virologic failure.

Missing Data Imputation for PRO Questionnaires

The handling of missing data for patient reported outcomes (PROs) will be as follows. If a respondent answers at least 50% of the items in a multi-item scale of the PedsQL, the missing items will be imputed with the average score of the answered items in the same scale. In cases where the respondent did not answer at least 50% of the items, the score for that dimension will be considered missing.

Regardless of the imputation method described above, if a subject starts another treatment for HCV, then all PRO data for this subject measured on or after the start date of the new HCV treatment will be excluded from analyses.

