10.0 Efficacy Analysis

10.1 General Considerations

General Considerations

All efficacy analyses will be performed on the ITT population, unless otherwise specified.

Missing data will be imputed as described in Section 6.3 for analyses of the HCV RNA endpoints of SVR.

Plasma HCV RNA levels will be determined for each sample collected by the central laboratory using the Roche COBAS® AmpliPrep/COBAS® TaqMan® HCV Quantitative Test, v2.0. The lower limit of detection (LLOD) and lower limit of quantification (LLOQ) for this assay (regardless of genotype) are both 15 IU/mL.

HCV RNA results that are detectable but not quantifiable are reported as "< 15 IU/ML HCV RNA DETECTED" and those that are undetectable are reported as "HCV RNA NOT DETECTED" in the database.

The notation "HCV RNA < LLOQ" is used to represent all HCV RNA values < 15 IU/mL, including values reported as "HCV RNA NOT DETECTED" or "< 15 IU/ML HCV RNA DETECTED." HCV RNA \geq LLOQ are all quantifiable values of 15 IU/mL or greater.

Definitions for Efficacy Endpoints

A confirmed quantifiable value during treatment is defined as any two consecutive HCV RNA measurements \geq LLOQ (or 100 IU/mL for **Breakthrough**), either both during treatment or at the final treatment measurement and the next consecutive post-treatment measurement. A confirmed quantifiable post-treatment value is defined as any two consecutive post-treatment HCV RNA measurements \geq LLOQ.

Breakthrough = confirmed HCV RNA \geq 100 IU/mL after HCV RNA < LLOQ during the Treatment Period; or confirmed increase from nadir in HCV RNA (two consecutive HCV RNA measurements $> 1 \log_{10}$ IU/mL above nadir) at any time point during the Treatment Period. A single breakthrough value (\geq 100 IU/mL or $> 1 \log_{10}$ above nadir) followed by lost to follow-up also will be considered a breakthrough (i.e., will not require confirmation).

EOT failure = HCV RNA \geq LLOQ at end of treatment with at least 6 weeks of treatment, where the HCV RNA value must be collected on or after Study Drug Day 36 and study drug duration \geq 36 days.

On-treatment virologic failure = **Breakthrough** or **EOT failure**; if a subject meets both definitions of Breakthrough and EOT failure, he or she will be categorized as Breakthrough only.

SVR₄ = HCV RNA $<$ LLOQ in the SVR₄ window (4 weeks after the last actual dose of study drug) without any confirmed quantifiable (\geq LLOQ) post-treatment value before or during that SVR window.

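### SAP 10.7 scores lost follow-up as SVR12/SVR24 discordance, and the protocol's relapse-after-SVR12 rate with its confidence interval is not planned

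*SAP*

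**What the plan says.** **Concordance.** SAP 10.7 assesses SVR12 against SVR24 by agreement, PPV and NPV, and SVR4 against SVR12 in the same way. For PPV: "The PPV of SVR₁₂ on SVR₂₄ is the proportion of subjects who achieve SVR₂₄ out of all subjects who achieved SVR₁₂". For agreement: "The agreement between SVR₁₂ and SVR₂₄ is a percentage defined as the number of subjects achieving both SVR₁₂ and SVR₂₄", together with the number achieving neither. No denominator is written for agreement; the section's opening line points to the ITT population.

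**Missing data.** SAP 10.1 states: "Missing data will be imputed as described in Section 6.3 for analyses of the HCV RNA endpoints of SVR". Section 6.3 then gives three steps. Backward imputation: "if the nearest HCV RNA value after the SVR window is unquantifiable or undetectable, then it will be used to impute" the value in the window. Next, if still missing, "then this value will be imputed with an HCV RNA value from a local laboratory if present". Finally: "Subjects with missing HCV RNA data in the analysis window, after imputations, will be imputed as a failure". SAP Table 4 sets the SVR12 window at Study Drug End Days 57 to 126 and the SVR24 window at Days 127 to 210.

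**Late relapse.** Protocol 8.1.2.3, item 4, lists the percentage of subjects who relapse after achieving SVR12, by age group and overall, and the section asks for Wilson 95% intervals on all rates. The rates listed in SAP 10.7 are HCV RNA below LLOQ by treatment visit, SVR12 by age group, SVR4 and SVR24. For relapse it plans a summary of treatment completers "displaying the number of subjects relapsing overall and by SVR visit window", and a listing for those who stopped treatment early. SVR24 non-response is given as number and percentage by reason, and Relapse24 and missing follow-up are separate reasons (SAP 10.1). SAP 12.1, which lists departures from the protocol, does not mention item 4.

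**The concern.** Missing-as-failure is a sensible convention for an SVR rate. Concordance asks something else: whether a negative result at Week 12 predicts a negative result at Week 24. On imputed status, a child who is negative at Week 12 and then leaves the study counts as a wrong prediction, although no virus was found. The SAP restricts to observed data elsewhere. The on-treatment item in the same section is reported "at each post-baseline visit in the Treatment Period (using data as observed) by age group and overall", and Relapse24 requires HCV RNA data in the SVR24 window. The concordance paragraph has no such condition.

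Subjects are followed for 144 weeks partly to assess durability of SVR12, and item 4 is the protocol's direct rate for that. As the SAP stands, the concordance figures partly measure retention, and the late-relapse rate would be reported without its own denominator or interval.

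**Working it through.** Neither document states a PPV, an agreement figure or a dropout rate, so there is no plan figure to reproduce.

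**Step 1: apply SAP 6.3 to simple patterns.**

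| HCV RNA pattern | SVR12 | SVR24 | Counted as |
|---|---|---|---|
| Negative Week 12, negative Week 24 | yes | yes | agreement |
| Negative Week 12, Week 24 missed, negative Week 36 | yes | yes (rescued) | agreement |
| Negative Week 12, no usable value afterwards | yes | no | disagreement, no virologic event |
| Week 12 missed, negative Week 24 | yes (back-imputed) | yes | agreement by construction |
| Week 12 missed, no usable value afterwards | no | no | agreement; raises NPV |

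The distortion runs both ways. The downward effect on PPV comes only from the third pattern.

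**Step 2: size of the downward effect.** Inputs: N = 125 (protocol 8.2). The SVR12 rate is assumed to be 97.8%, borrowed from the adult treatment-naïve plus TE-PRS result of 2206/2256 in protocol Table 3. Then 0.978 × 125 = 122.3, so R = 122 responders and NR = 3 non-responders, who also fail SVR24. No relapse or reinfection occurs after SVR12. Let k be the responders with no usable HCV RNA from Day 127 on; the values of k are assumptions.

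- PPV under the SAP = (R − k)/R
- Agreement under the SAP = (R − k + NR)/N, taking all 125 as denominator
- PPV leaving out failures due only to missing data = (R − k)/(R − k)

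| k | PPV, SAP | Agreement, SAP | PPV, missing-only failures excluded |
|---|---|---|---|
| 3 | 119/122 = 97.5% | 122/125 = 97.6% | 119/119 = 100% |
| 6 | 116/122 = 95.1% | 119/125 = 95.2% | 116/116 = 100% |
| 12 | 110/122 = 90.2% | 113/125 = 90.4% | 110/110 = 100% |

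**Step 3: what the absent interval would show.** With zero events the Wilson 95% upper limit is z²/(n + z²), where z² = 3.84.

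- Overall, n = 119, 116 or 110: 3.1%, 3.2% or 3.4%.
- n = 47 (adolescents treated in Part 1, protocol 3.0): 3.84/50.84 = 7.6%.
- n = 27 (81/3, about one Part 2 age group, protocol 5.1): 3.84/30.84 = 12.5%.
- n = 22 (final-dose target per Part 2 age group, protocol 5.5.3): 3.84/25.84 = 14.9%.

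The 47, 27 and 22 are treated or planned numbers. Responders with later data will be fewer, so the limits will be wider; for n = 26 the limit is 12.9%.

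**Step 4: does another planned output supply item 4?** Relapse12 carries a Wilson interval but stops at the SVR12 window. Relapse24 covers one window and appears only as a reason for SVR24 non-response. Relapse_overall runs to the last post-treatment value but is given as counts by window among treatment completers. None has SVR12 responders as denominator with an interval.

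**The case against.** Using one pre-specified rule for every SVR endpoint keeps the concordance table consistent with the SVR tables. Protocol 8.1.2.3 does not list concordance, so the SAP breaks no protocol commitment there. That stands: the choice is permitted, but it answers a mixed question.

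The loss figures have no source in the documents, and a responder must miss every usable value from Day 127 on to count. HCV RNA is scheduled at Post-Treatment Weeks 24, 36, 48, 96 and 144 and at premature discontinuation, and local-laboratory values can also rescue. This stands too; 12 losses may be extreme.

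A reader might infer that the SAP shows late relapse only as bare counts, or hides missing data behind apparent relapse. The documents do not support that. SVR24 non-response is tabulated as number and percentage by reason, with relapse, reinfection, early discontinuation and missing data kept apart. A crude responder-based rate could also be worked out from the relapse counts and the SVR12 table. What is lacking is narrower: the SVR12-responder denominator, the interval, and a percentage for relapse after the SVR24 window.

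A reader might also infer that the sponsor dropped item 4 deliberately. The SAP elaborates Amendment 1 of 25 July 2017, whose wording of 8.1.2.3 is not available, so a version gap is possible. The current change list shows only a title change for that section, which does not settle when item 4 entered.

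**Conclusion.** Both parts hold, within limits. First, agreement, PPV and NPV in SAP 10.7 rest on status after missing-as-failure imputation. SVR12 responders with no usable HCV RNA from Day 127 on lower PPV and agreement without a virologic event; subjects missing at both windows raise agreement and NPV. The same mechanism applies to SVR4 against SVR12. The reading follows from SAP 6.3 and 10.1, because the concordance paragraph itself is silent on imputation. In the illustration each lost responder costs about 0.8 percentage points of PPV (1/122). The true loss is unknown, and the figures assume an adult SVR12 rate and no late relapse.

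Second, the current protocol's relapse-after-SVR12 percentage with Wilson interval has no planned counterpart in the SAP. This is the firmer part, since it concerns a listed endpoint.

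It would be wrong to read this as a bias in the main results. Primary PK, SVR12, the secondary endpoints and safety are untouched. The changes are worth making because they are cheap, and because a zero count within one age group is compatible with a late-relapse rate above 10%.

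**What to change.** In SAP 10.7:

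(a) Beside the imputed concordance, report agreement, PPV and NPV excluding only subjects whose SVR failure at either time point is due solely to missing HCV RNA. Keep known virologic failures (including a missed Week 24 visit followed by quantifiable RNA), subjects who started other HCV treatment, and backward-imputed negatives. State the denominator and the number excluded, and write the denominator for the imputed agreement as well. Do the same for SVR4 against SVR12. Requiring an observed value in both windows would be too strict: it would drop known failures and properly rescued subjects.

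(b) Add the protocol item 4 rate: relapse after SVR12 through the last post-treatment visit under the SAP 10.1 relapse rule, with reinfection reported separately. The protocol writes no denominator. A workable one is SVR12 responders with at least one HCV RNA value after the one that determined SVR12. Give it by age group and overall, with the Wilson 95% CI and the number still observed at Weeks 24, 48, 96 and 144.

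The cost is SAP wording and one extra table; the data are already collected. The downside is slightly smaller denominators, with an NPV that may rest on very few subjects, and an assumption that loss is unrelated to relapse. For that reason the imputed version should stay beside the new one.
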